7.4 Screening failures

For screening failures the following must be collected: reason for not continuing in the trial, SAEs and AEs. Follow-up of SAEs must be carried out according to section 9.5.

7.5 Subject Enrolment Log

All subjects screened for this trial will be recorded on an enrolment log. The log will record whether subjects were enrolled or not. If a subject is not enrolled, the main reason for non-

enrolment will be listed. The log will be prepared according to local regulations regarding personal data protection.

Additionally, all subjects that fail screening will be accounted for in the electronic case report form (eCRF). These subjects will be identified by a subject ID and date or year of birth.

7.6 Subject Identification List

The (sub)investigator must maintain a list of all subjects entering the open-label phase at the trial site including each subject's identity, date of enrolment and corresponding subject ID so that any subject may be identified if required for any reason. The list is kept by the investigator and must not be copied or retained by LEO.

At screening visit, each subject must be assigned a unique subject ID to protect the subject's identity and which will be used in lieu of the subject's name when the (sub)investigator reports trial-related data.

The subject ID is distinct from the randomisation code number.

7.7 Subject card

At screening, subjects will be provided with a card stating that they are participating in a trial and giving contact address(es) and telephone number(s) of relevant trial site staff.

7.8 Restrictions during Trial

Use of concomitant treatment must be recorded in the subject's medical record and the eCRF (treatment/drug name, dose, indication and dates of start and stop).

7.8.1 Restrictions prior to the start of treatment (Visit 1)

The washout phase is up to 4 weeks (28 days). Subjects who are being treated with medications requiring more than 4 weeks washout will not be eligible for the trial.

However, subjects might be eligible if they had a treatment-free period prior to entering the trial (i.e. having signed the Informed Consent).

Note: the treatment-free period prior to entering the trial is not a trial related procedure and accordingly not part of the trial defined wash-out phase. The earliest possible wash-out start date to record in the eCRF is the day the subject entered the trial (i.e. having signed the Informed Consent).

To account for an adequate treatment-free period, the date of last use of the excluded medication will be recorded in the eCRF.

Treatments requiring washout

Treatments requiring washout before Visit 1 are listed in [Table 1](#) (all subjects) and [Table 2](#) (subjects performing HPA axis test) below, together with the required individual washout periods.

7.8.2 During the Trial Treatment Phase (open-label treatment phase and maintenance phase)

Treatments which cannot be used during the treatment period (Visit 1 to Visit 15) are listed in [Table 1](#) (applicable to all subjects).

Table 1: Prohibited Medication including Non-Drug Therapies and Procedures (for all subjects)

Prohibited Medication including Non-Drug Therapies and Procedures	Location	Exclusion Period Restrictions
Systemic treatment with biological therapies (marketed and not marketed), with a possible effect on psoriasis vulgaris	Not applicable	
 Etanercept: within 4 weeks prior to Visit 1 Adalimumab, infliximab: within 8 weeks prior to Visit 1 Ustekinumab: within 16 weeks prior to Visit 1 Secukinumab: within 12 weeks prior to Visit 1 Other products: within 4 weeks/5 half-lives prior to Visit 1 (whichever is longer) and any time during the trial treatment phase
Systemic treatment with therapies other than biologicals, with a possible effect on psoriasis vulgaris (e.g., corticosteroids, retinoids, methotrexate, cyclosporin and other immunosuppressants)	Not applicable	Within 4 weeks prior to Visit 1 and any time during the trial treatment phase
Systemic treatment with apremilast	Not applicable	Within 4 weeks prior to Visit 1 and any time during the trial treatment phase
Use of non-marketed/other IPs	Body and scalp	Within 4 weeks or 5 half-lives (whichever is longer) prior to visit 1 and any time during the trial treatment phase
Psoralen combined with UVA therapy (PUVA)	Body and scalp	Within 4 weeks prior to Visit 1 and any time during the trial treatment phase
UVB therapy	Body and Scalp	Within 2 weeks prior to Visit 1 and any time during the trial treatment phase
Any topical treatment on the body or scalp	Body and	Within 2 weeks prior to visit 1 and any time

Prohibited Medication including Non-Drug Therapies and Procedures	Location	Exclusion Period Restrictions
including corticosteroids (except for emollients, non-steroid medicated shampoos and low potency corticosteroids on sensitive areas), see Table 3	Scalp	during the trial treatment phase. On areas treated with IP, emollients should not be used on days where IP is being applied.
Initiation of, or changes to, concomitant medication that could affect psoriasis vulgaris (e.g. beta-blockers, lithium, anti-malaria drugs, ACE inhibitors)	Not applicable	Any time during the trial treatment phase
Vitamin D supplements > 400 IU/day, (note: stable dose of vitamin D supplements ≤ 400 IU/day is permitted)	Not applicable	Any time during the trial treatment phase
Excessive exposure of treated areas to either natural or artificial sunlight that may affect psoriasis vulgaris. (i.e., normal lifestyle outdoor activities are permitted but deliberate exposure to sunlight or artificial ultraviolet light like tanning booths should be avoided)	Body and Scalp	Any time during the trial treatment phase

For subjects performing HPA axis test, additional treatments requiring washout before Visit 1 and prohibited during the trial are listed in [Table 2](#) below, with the required individual washout periods:

Table 2: Prohibited Medication including Non-Drug Therapies and Procedures (for subjects performing HPA axis test)

Prohibited Medication including Non-Drug Therapies and Procedures	Location	Exclusion Period Restrictions
Systemic treatment with corticosteroids	Not applicable	Within 12 weeks prior to V1 and any time during the trial treatment phase
Inhaled corticosteroids	Not applicable	Within 4 weeks prior to V1 and any time during the trial treatment phase
Oestrogen therapy (including contraceptives) or any other medication known to affect cortisol levels or HPA axis integrity	Not applicable	Within 4 weeks prior to V1 and any time during the trial treatment phase
Enzymatic inductors (e.g., barbiturates, phenytoin, rifampicin), systemic or topical cytochrome P450 inhibitors (e.g., ketoconazole, itraconazole, metronidazole), hypoglycaemic sulfonamides, antidepressive medications	Body and Scalp	Within 4 weeks prior to V1 and any time during the trial treatment phase
Topical ketoconazole	Body and Scalp	Within 2 weeks prior to V1 and any time during the trial treatment phase

For all subjects, a stable concomitant treatment regimen with other drugs that have a potential effect on psoriasis (e.g. beta-blockers, anti-malarials and ACE inhibitors) is allowed during the trial.

Inhaled steroids are allowed during the trial (except during the last 4 weeks prior to ACTH-challenge for subjects participating in the HPA axis part).

Bath oils and moisturising soaps are allowed during the trial.

Sunscreens are allowed but should not be applied at the same time as the trial medication (an interval of at least 1 hour is recommended between applications).

Any skin conditions other than psoriasis may be treated with topical therapy as appropriate provided the treatment does not affect the assessment, treatment or severity of psoriasis. The topical therapy should be applied only on the target area(s) of the skin condition and not on the area(s) of psoriasis.

Concomitant anti-psoriatic treatments allowed during the trial is listed in [Table 3](#):

Table 3: Permitted concomitant anti-psoriatic treatment

Location	Permitted concomitant anti-psoriatic treatment
Scalp	Non-medicated and medicated shampoos/products except those that contain corticosteroids or vitamin D analogues (e.g., tar, salicylic acid, tazarotene, anthraline) are allowed. Topical use of mild corticosteroids (class 6-7) is allowed, but should be for short term use and be minimized to the largest possible extent.
Trunk/limbs	Bath oils and moisturizing soaps are allowed. Unlimited use of emollients (except within 6 hours of clinic visits) is allowed. Emollients used should not contain alpha-hydroxy acids, beta-hydroxy acids or acetylic acid; Emollients containing urea acid ($\leq 5\%$) are allowed.
Face and sensitive areas	Any topical treatments other than class 1-5 corticosteroids or Vitamin D analogues (calcipotriol, calcitriol or tacalcitol) are allowed (e.g. topical calcineurin inhibitors). Topical use of mild corticosteroids (class 6-7) is allowed, but should be for short term use and be minimized to the largest possible extent. Unlimited use of emollients is allowed. Bath oils and moisturizing soaps are allowed.

Note: sensitive areas refers to armpits, groin, under the breasts and in other skin folds around the genitals and buttocks

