5.3 Safety assessments

- Adverse events of concern associated with long-term corticosteroid use
- Incidence of rebound (as defined in section [11.3.6.2](#))
- Local safety and tolerability assessment scores
- Effect on calcium metabolism, based on change from baseline in serum calcium and spot urinary calcium at Week 4 and the end of trial
- Effect on HPA axis (in a subset of subjects with disease involvement of between 10 and 30% of BSA), based on serum cortisol ≤ 18 mcg/dL 30 minutes after cosyntropin injection at Week 4, Week 28, and end of trial (Week 56) or early withdrawal.

[figure not shown]
Exposure and standard safety data will be reported as described in sections [11.3.3](#) and [11.3.6](#).

6 Trial Design

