6.1.4.1 Relapse at a regular 4-week (scheduled) visit

[figure not shown]
In case a relapse of psoriasis (defined as PGA of at least 'mild') is observed by the investigator at a regular monthly visit, the subject will be provided with rescue IP and instructed to apply it on the affected areas on trunk and limbs once daily for 4 weeks (all active psoriatic lesions including any new areas that become active during this 4-week treatment period).

Twice weekly maintenance treatment will continue unchanged on areas that are not active.

The subject will return to the trial site 4 weeks later to attend the regular monthly visit, where, if the subject is 'clear' or 'almost clear' according to PGA, maintenance treatment will be resumed on those areas. If the PGA of 'clear' or 'almost clear' is not achieved after 4 weeks of rescue treatment, the subject will exit the trial. For illustration, see Figure 2 below.

Figure 2 Relapse at a regular 4-week (scheduled) visit

6.1.4.2 Relapse between regular 4-week (scheduled) visits – more than one week prior to the next regular visit

If, in the opinion of the subject, a relapse of psoriasis occurs between regular visits when there is more than one week (7 days) to the next planned visit, the subject will contact the trial site to be assessed by the investigator at an unscheduled visit.

If relapse is confirmed by the investigator, the subject will be provided with rescue IP and instructed to apply it once daily for 4 weeks on any active psoriatic lesions on trunk and limbs during this time.

[figure not shown]
Twice weekly maintenance treatment will continue unchanged on areas that have not relapsed.

The subject will be examined at the next regular 4-week visit, but even if ‘clear’/‘almost clear’ at the regular visit, rescue treatment will continue. A relapse follow-up visit will take place at a relapse follow-up visit 4 weeks after the unscheduled visit where relapse treatment was initiated. If the subject is ‘clear’ or ‘almost clear’ according to PGA at this relapse follow-up visit, maintenance treatment on those areas will be resumed and the subject will follow the planned visit schedule.

If the subject is not ‘clear’ or ‘almost clear’ according to PGA after 4 weeks of relapse treatment, they will exit the trial. For illustration, see [Figure 3](#) below.

Figure 3 Relapse between regular 4-week (scheduled) visits – more than one week prior to the next regular visit

[figure not shown]

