6.1.5 Follow-up Phase

There are three types of follow-up visits, here listed in chronological order:

Follow-up Visit 1 (FU1):

A follow up visit 1 is only relevant for subjects with an ongoing AE at end of treatment. A follow-up visit/contact (FU1) should be conducted 14 (\pm 2) days after the last on-treatment visit (Visit 15/Early Withdrawal), unless the final outcome of the event, as defined below, has been determined before then.

This follow-up visit/contact (FU1) will take place only if:

1. there is an on-going SAE at the last on-treatment visit.
2. there is an on-going non-serious AE at the last on-treatment visit which is classified as possibly or probably related to the IPs
3. the albumin-corrected serum calcium is above the reference range at the last on-treatment visit
4. the calcium:creatinine ratio is above the reference range and clinically significant at the last on-treatment visit

Where the (sub)investigator considers it appropriate, the Follow-up Visit may be performed as a telephone contact. If a subject also is eligible for a follow up visit 2 (FU2), the follow-up on the ongoing AE can wait until FU2 (see below).

Follow-up Visit 2 (FU2):

For subjects undergoing the adrenocorticotropic hormone (ACTH) challenge test, a follow-up visit (Visit FU2) will take place 28 days after the ACTH challenge test performed at the end of treatment (Visit 15/Early Withdrawal) if the end of treatment test shows a serum cortisol concentration ≤ 18 mcg/dl at both 30 minutes and 60 minutes after ACTH challenge (39, 40).

If the results of the ACTH challenge test at Visit FU2 continue to show a serum cortisol concentration ≤ 18 mcg/dl at both 30 minutes and 60 minutes after ACTH challenge, further ACTH challenge tests should be performed, but not more often than at 4-weekly intervals, until the adrenal suppression resolves (i.e. serum cortisol concentration > 18 mcg/dl at 30 minutes or at 60 minutes after the ACTH-challenge, or at both time-points).

Refer to Section 8.12.1 for further details on the ACTH challenge test.

Follow-up visits should be performed within ± 4 days of the scheduled time; if they are outside this window, the (sub)investigator should record the reason in the subject's medical record but LEO do not need to be notified.

Follow-up Visit 3 (FU3):

All subjects should be followed up for events of rebound for 8 weeks after last application of IP. The different scenarios are outlined below:

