15. Planned excessive exposure of area(s) to be treated with trial medication to either natural or artificial sunlight (including tanning booths, sun lamps etc.) during the trial
16. Known or suspected disorders of calcium metabolism associated with hypercalcaemia
17. Known or suspected hypersensitivity to component(s) of investigational products
18. Current participation in any other interventional clinical trial
19. Previously screened in this trial
20. In the opinion of the (sub)investigator, the subject is unlikely to comply with the clinical trial protocol (e.g. due to alcoholism, drug addiction or psychotic state)
21. Females who are pregnant, wishing to become pregnant during the trial or are breastfeeding
22. Subjects in close affiliation with the trial personnel (e.g. immediate family member or subordinate), subjects being a member of the clinical trial personnel, or being an employee of the sponsor or a contract research organization (CRO) involved in the trial
23. Subjects who are institutionalized by court order or by local authority.

Additional exclusion criteria for subjects undergoing HPA axis test (assigned sites only):

24. A history of allergic asthma, serious allergy or serious allergic skin rash

25. Known or suspected hypersensitivity to component(s) of CORTROSYN® (including cosyntropin/tetracosactide) (in the US) / Synacthen® (including tetracosactide) (in Europe)
26. The use of inhaled corticosteroids in the 4 weeks prior to Visit 1 or during the trial
27. Systemic corticosteroid treatment in the 12 weeks prior to Visit 1 or during the trial
28. Enzymatic inductors (e.g., barbiturates, phenytoin, rifampicin) within 4 weeks prior to Visit 1 or during the trial
29. Systemic or topical cytochrome P450 inhibitors (e.g., ketoconazole, itraconazole, metronidazole) within 4 weeks prior to Visit 1 or during the trial. Topical ketoconazole within 2 weeks prior to Visit 1
30. Hypoglycemic sulfonamides within 4 weeks prior to Visit 1 or during the trial
31. Antidepressive medications within 4 weeks prior to Visit 1 or during the trial.
Oestrogen therapy (including contraceptives), antidepressant medications and any other medication known to affect cortisol levels or HPA axis integrity within 4 weeks prior to baseline
32. Not following nocturnal sleep patterns
33. Any of the following conditions, whether known or suspected:

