7.9 Discontinuation

Subjects **may** withdraw from the trial for any of the following reasons:

1. *Screening failure*
2. *Lack of efficacy:* The (sub)investigator is free to withdraw the subject at any time based on a medical judgement.

3. *Adverse event (please specify):* Any adverse event (AE) that the (sub)investigator considers unacceptable.
4. *Withdrawal by subject:* Subjects are free to withdraw from the clinical trial at any time and for any reason.
5. *Lost to follow-up*
6. *Death*
7. *Other (please specify):* Other reasons than stated above which require the subject to (be) withdraw(n) should be specified.

Subjects **must** be withdrawn from the trial for any of the following reasons:

8. *Subjects who do not achieve treatment success (PGA score of 'clear' or 'almost clear' with at least a 2-grade improvement from baseline) after initial 4-week treatment*
9. *Subjects who are not scored as 'clear' or 'almost clear' after 4-week treatment of relapse*

If adverse event or other is selected, a specification must be supplied.

Subjects who are discovered, after enrolment/randomisation, not to have fulfilled all in-/exclusion criteria at the time of enrolment should discontinue treatment unless the (sub)investigator, based on clinical and ethical evaluation, finds discontinuation inappropriate.

The final efficacy assessment (at the correct scheduled time) should be attempted to be completed for all subjects. Such deviation(s) from the (Consolidated) Clinical Trial Protocol must be reported to LEO Pharma A/S (and Independent Ethics Committee (IEC)/Institutional Review Board (IRB), as appropriate) and recorded in the Clinical Study Report.

Reason(s) for discontinuation from trial will be recorded in the eCRF. Subjects withdrawn will not be substituted.

8 Trial Schedule and Assessments

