The ACTH-challenge test will be performed at baseline (Visit 1), after 4 weeks (Visit 2), after 28 weeks (Visit 8) and at the end of trial (Visit 15 or at early withdrawal). If the subject withdraws prior to completing the initial open-label treatment phase, the ACTH-challenge test scheduled for Visit 2 should not be performed. If the subject discontinues the trial prior to week 56 (this also includes discontinuation due to not achieving 'clear' or 'almost clear' disease status following 4 weeks of once daily treatment following a relapse in psoriasis status), a follow-up visit must be scheduled within 7 days of the last treatment period visit for the purpose of performing the ACTH-challenge test, if the test was not performed on the same day (rescheduling required due to the time dependency of the ACTH-challenge test).

Subjects will not be included in this procedure of the trial if one of the following applies to the serum cortisol concentration at Visit 1:

- ≤ 5 mcg/dl pre-stimulation (before CORTROSYN® / Synacthen® injection)
- ≤ 18 mcg/dl at 30 minutes after CORTROSYN® / Synacthen® injection

If the ACTH challenge test at Visit 15 (end of maintenance phase) or at early withdrawal shows a serum cortisol concentration ≤ 18 mcg/dl at both 30 minutes and 60 minutes after the ACTH challenge, a further ACTH-challenge test is required 4 weeks later (FU2 visit).

If the results of the ACTH-challenge test at the FU2 visit continue to show a serum cortisol concentration ≤ 18 mcg/dl at both 30 minutes and 60 minutes after ACTH challenge, further ACTH challenge tests should be performed, but not more often than at 4-weekly intervals, until the adrenal suppression resolves (i.e. serum cortisol concentration > 18 mcg/dl at 30 minutes or at 60 minutes after the ACTH challenge, or at both time-points). The data from such further ACTH challenge tests must be captured in the unscheduled follow-up visit page in the eCRF.

The following procedures should be performed prior to the ACTH challenge tests: Heart rate and blood pressure, blood/urine sampling for central laboratory analysis (biochemistry/urinalysis), blood sampling for biomarkers and urine pregnancy test (in female subjects of child-bearing potential).

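### For subjects in the HPA part, the protocol gives two conflicting rules on inhaled corticosteroids: banned throughout treatment, or barred only in the 4 weeks before an ACTH challenge

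*Protocol*

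**What the plan says.** Three provisions of the current protocol deal with inhaled corticosteroids in HPA subjects.

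- **Section 7.3, exclusion criterion 26** (HPA subjects only) excludes "The use of inhaled corticosteroids in the 4 weeks prior to Visit 1 or during the trial".
- **Section 7.8.2, Table 2** (HPA subjects only) has a row for inhaled corticosteroids with the restriction "Within 4 weeks prior to V1 and any time during the trial treatment phase". The lead-in says the listed treatments are prohibited in the trial as well as washed out beforehand.
- **Section 7.8.2, text below Table 2** states: "Inhaled steroids are allowed during the trial (except during the last 4 weeks prior to ACTH-challenge for subjects participating in the HPA axis part".

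Section 5.3 bases the HPA safety assessment on cortisol after ACTH stimulation "at Week 4, Week 28, and end of trial (Week 56) or early withdrawal". For a subject who stops before Week 56 and was not tested on the same day, section 8.12.1 says "a follow-up visit must be scheduled within 7 days of the last treatment period visit for the purpose of performing the ACTH-challenge test". Under section 6.1.5, if cortisol is low at both 30 and 60 minutes, "a follow-up visit (Visit FU2) will take place 28 days after the ACTH challenge test performed at the end of treatment (Visit 15/Early Withdrawal"). SAP section 5.5.7 lists ACTH results from early-termination visits and leaves them out of its tables and figures.

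**The concern.** A site reading criterion 26 or Table 2 would refuse an inhaled corticosteroid to an HPA subject at any time in treatment. A site reading the later sentence would allow it between test windows. Whether such use is a protocol deviation depends on which text is applied.

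The HPA part asks whether LEO 90100 suppresses the adrenal axis. A second corticosteroid confuses that question if it is in use shortly before a test. Scheduled tests are protected under both rules. A withdrawal test may not be, because section 7.9 provides that "Subjects are free to withdraw from the clinical trial at any time and for any reason" and the test follows on the day or within a week. If inhaled use was permitted until then, there is often no time for 4 clean weeks. A low cortisol at such a test could come from the inhaled drug and could also trigger the FU2 retest.

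**Working it through.** **Can the texts be reconciled?**

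| Provision | Who it covers | Inhaled use between test windows |
|---|---|---|
| Criterion 26 | HPA subjects | Excluded |
| Table 2 row | HPA subjects | Banned |
| Sentence below Table 2 | All subjects, with an exception for HPA subjects | Allowed |

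The sentence cannot be confined to non-HPA subjects, because its exception is written for HPA subjects. A rule that the specific text prevails does not help, because criterion 26 and Table 2 are equally specific.

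**Weeks in which the rules differ.** Treatment runs from Week 0 to Week 56, with on-treatment tests at Weeks 4, 28 and 56 (section 8.12.1).

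- Barred by the sentence: Weeks 0–4, 24–28 and 52–56, so 3 × 4 = 12 weeks.
- Permitted by the sentence: 56 − 12 = 44 weeks (Weeks 4–24 and 28–52), or 44/56 = 79%.
- Permitted by criterion 26 and Table 2: 0 weeks.

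**Ceiling on the number of tests exposed.** The inputs are the aim of about 25 HPA subjects tested after 52 weeks of exposure and the 30% exponential drop-out over 52 weeks, both from section 11.1. The HPA subset is assumed to drop out at the same rate. With t in weeks since randomisation at Week 4:

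S(t) = 0.7^(t/52)

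This reproduces the protocol's own exposure figures: 380 × S(22) = 380 × 0.860 = 326.8 (protocol: 326) and 380 × S(48) = 380 × 0.7195 = 273.4 (protocol: 273). As in the protocol, 52 weeks of exposure means 48 weeks after randomisation.

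- Randomised HPA subjects needed: 25 / S(48) = 25 / 0.7195 = 34.7.
- All early withdrawals: 0.30 × 34.7 = 10.4.
- Withdrawals in permitted weeks (t = 0–20 and 24–48): [1 − S(20)] + [S(24) − S(48)] = (1 − 0.8718) + (0.8482 − 0.7195) = 0.257. Then 0.257 × 34.7 = 8.9.
- The remaining 10.4 − 8.9 = 1.5 fall in a barred window that has only partly run.

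Replacing 0.7 by 0.8 or 0.6 shows the sensitivity to drop-out:

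| Drop-out over 52 weeks | Randomised | Early withdrawals | In permitted weeks |
|---|---|---|---|
| 20% | 30.7 | 6.1 | 5.2 |
| 30% | 34.7 | 10.4 | 8.9 |
| 40% | 40.1 | 16.0 | 13.8 |

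These counts treat every withdrawal as tested and at short notice, so they overstate. Loss to follow-up, death and some withdrawals of consent give no test. Exits after failed rescue are not at short notice: if clear or almost clear "is not achieved after 4 weeks of rescue treatment, the subject will exit the trial" (section 6.1.4.1), so the possible exit date is known when rescue starts, 4 weeks earlier.

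**The case against.** The strongest reply is that this is a drafting slip with little consequence.

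- **The sentence is a permission.** A site that applies the ban breaches nothing. Another Table 2 row also bans other drugs that affect cortisol or the HPA axis. Both are true, but a site that relies on the permission is also following the protocol as written, and the extra row only adds to the conflict.
- **Few subjects could be users.** Criterion 26 excludes use in the 4 weeks before Visit 1, and criterion 24 excludes a history of allergic asthma. Only subjects who start or resume during the trial matter. This stands, and the counts above do not allow for it: they count withdrawals, not users.
- **The bound depends on definition.** On a strict count of tests that might lack 4 full clean weeks, the ceiling is all 10.4 withdrawals; 8.9 is the part for which no clean period has begun. The distinction is fair and does not affect the conflict.
- **No planned summary changes.** The SAP keeps early-termination ACTH results out of its tables, and a falsely low cortisol would err towards finding suppression. This stands. However, section 5.3 of the protocol still counts those tests, and a low result can still bring a subject back for FU2.
- **Attribution is already possible.** Concomitant medication is recorded with dates (section 8.8) and listed (SAP Listing 4-6). A careful reader could therefore cross-check, which is a further reason to rate the point low.

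**Conclusion.** The concern holds, as a minor one. The 7.8.2 sentence contradicts criterion 26 and Table 2 for HPA subjects over 44 of 56 treatment weeks, and nothing in the protocol settles which governs. This follows from the text alone.

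The practical reach is narrow: short-notice early-withdrawal tests in HPA subjects who took up inhaled corticosteroids during the trial. At most about 9 of about 35 randomised HPA subjects withdraw in permitted weeks (about 5 to 14 at 20% to 40% drop-out), assuming the subset follows the trial-wide exponential drop-out. The documents do not say how many would be using an inhaled steroid. Sample size, efficacy analyses and the SAP's HPA summary tables are unaffected.

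**What to change.** Reword the 7.8.2 sentence so that its permission covers only subjects outside the HPA part, and refer HPA subjects to Table 2. For example: *Subjects who are not in the HPA axis part may use inhaled steroids; HPA subjects follow Table 2.*

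Relaxing criterion 26 and Table 2 to the 4-week rule would also remove the contradiction. It would leave short-notice withdrawal tests unprotected, so the ban is the better choice.

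Optionally, mark recorded inhaled corticosteroid use in SAP Listing 8-7, next to the ACTH results. This still helps if conduct is too far advanced for a protocol amendment.

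The cost is one changed sentence. The optional mark uses concomitant-medication data already collected.
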